### 3.2 Exclusion Criteria

1. Patients may not be receiving any other investigational agents while on study
2. Patients who have known allergy to posaconazole or other azoles (for study drug arm only)
3. Patients who have previously had a severe side effect, such as agranulocytosis and neutropenia, in conjunction with previous azole class drugs for a parasitic infection (for study drug arm only)
4. Patients with a history of acute or chronic hepatitis (for study drug arm only)

5. Patients with liver enzymes (ALT, AST, ALP) >1.5x above normal range for the laboratory performing the test (for study drug arm only)
6. Patients who are taking metronidazole and cannot be safely moved to a different antibiotic greater than 7 days prior to starting posaconazole therapy (for study drug arm only)
7. Patients who are taking any anti-convulsant medication that interferes with the cytochrome P450 pathway (e.g. phenytoin, phenobarbital, carbamazepine, etc.) and who cannot be switched to alternative medications such as Keppra (levetiracetam) (for study drug arm only)
8. Uncontrolled intercurrent illness such as chronic hepatitis, acute hepatitis, or psychiatric illness/social situation that would limit compliance with study requirements (for study drug arm only)
9. Patients with a history of Addison's disease or other forms of adrenal insufficiency (for study drug arm only)
10. Patient with little or no stomach acid production (achlorhydria) (for study drug arm only)
11. Pregnant and breastfeeding women
12. Patients with a history of any medical or psychiatric condition or laboratory abnormality that in the opinion of the investigator may increase the risks associated with the study participation or investigational product administration or may interfere with the interpretation of the results.
13. Patients who are not available for follow-up assessments or unable to comply with study requirements
14. Patients who are currently taking medications that induce the metabolism of posaconazole, such as isoniazid, nevirapine, rifamycins (such as rifabutin, rifampin), or St. John's wort and cannot be safely discontinued off of them for the duration of the trial (for study drug arm only).

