### 7.2.1 Visit 1 (Screening and baseline)

Once informed consent has been obtained, the following are performed as **routine (standard) care** or data collected from the EMR if they were performed within 31 days of consent:

- Demographics.
- CBC and Comprehensive Metabolic Panel (which includes electrolytes, renal function and liver function) (approximately 2 teaspoons of blood).
- Medical history.
- Neurological examination.
- Baseline MRI Brain +/- Gadolinium contrast scan will be reviewed.
- Concomitant medications are reviewed.
- A 12-lead ECG.
- If a female of childbearing age, a pregnancy test will be performed.

Blood will be drawn for Comprehensive Metabolic Panel (CMP) **for the study drug group only** (approximately 2 teaspoons of blood). Patients will wait at the clinic or emergency department if no urgent surgery or biopsy is indicated until these results are available (usually within 4 hours).

If the participant's routine tests show that they are eligible and their liver function tests are acceptable, they will be able to continue in the study.

If the patient is pregnant, confirmed by the pregnancy test, the medical team can take appropriate steps to ensure the safety of both the mother and the fetus, and the patient will not be able to continue study and will be considered a screen fail.

If any of routine tests or liver function tests are outside the acceptable ranges for the study, they will be assessed for candidacy in the ketoconazole study, which has a separate IRB-approved protocol (IRB# STUDY00014115). If enrollment in the ketoconazole study is already completed or if the participant is not a candidate for ketoconazole either, then they will be considered for possible candidacy in the control arm. If, in this scenario, 5 participants have already been

enrolled in the control arm then the patient will not be a candidate for this study and they will be considered a screen fail for this study. The study doctor will follow-up regarding any abnormal results for clinical purposes.

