### **7.2.2 Visit 2 (3 days +/- 2 days after starting the study drug)**

**This visit is ONLY for the study drug arm.** Participants will return to the clinic for a **research-only visit**. At this visit, the following will be performed:

- Collection of adverse events.
- A 12-lead ECG to rule out QTc prolongation
- Comprehensive Metabolic Panel (which includes electrolytes, renal function and liver function). Lab values within 1.5x institutional upper limit of normal are acceptable and not considered adverse events.

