#### **Study drug group**

The following will be performed as **routine (standard care)**:

- Neurological examination.

The following will be performed for the **research only**:

- Patient will take study medication at 8am +/- 4 hours and then study medication will be discontinued.
- Comprehensive Metabolic Panel (which includes electrolytes, renal function and liver function) (approximately 1 teaspoon of blood). Lab values within 1.5x institutional upper limit of normal are acceptable and not considered adverse events.
- Dialysate and blood sample collection.
- Collection of adverse events.

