##### Study drug group

The following will be performed as **routine (standard care)**:

- Neurological exam

The following will be performed for the **research only**:

- Collection of adverse events.

Samples collected during the study for research-only purposes will be sent for analysis as shown below:

Sample	Analysis location
Comprehensive Metabolic Panel (which includes electrolytes, renal function and liver function) at Visits 1, 2, and 5	Clinical laboratory
Tissue from biopsy or surgery	[name] laboratory (pharmacodynamics)
	Mass Spectrometry core at Penn State Hershey Cancer Institute (PSHCl) (metabolites and drug concentration)
Plasma at Visits 5 and 6	Mass Spectrometry core at PSHCl (drug concentration)
Dialysate at Visits 5 and 6	Mass Spectrometry core at Penn State Hershey Cancer Institute (PSHCl) (metabolites and drug concentration)

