### **Secondary Objectives**

- Tolerability: Adverse experiences observed over the 7-21 days of protocol follow-up will be characterized in CTCAE v5.0. Frequency and severity of AEs according to body system and severity criteria will be described. In addition, frequency of grade 3 or 4 adverse events will be described separately. Causality will also be noted. Laboratory assessments will also be described according to the NCI CTCAE, V 5.0 criteria, with separate descriptions for grade 3 or 4 laboratory abnormalities. Clinically significant laboratory abnormalities will be described as well.
- Pharmacodynamics: Descriptive statistics, using means/ median, will be used to report drug effect on:
  - a) HK2 activity in resected tumor tissue
  - b) Concentration of downstream glycolysis metabolites in resected tumor tissue

- c) Tumor cell proliferation, cell death, and angiogenesis in resected tumor tissue
- d) Concentration vs time profile of lactate and pyruvate, based on MDC studies, in relation to the concentration vs time profile of posaconazole.

\*\* The above values will be compared to levels in the control arm.

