### **10.0 Risks**

#### **Risk of drug**

While this drug has never been tested specifically in the HGG population, it is an FDA-approved drug. The potential side effects are:

Common side effects (occurring in at least 1 in 100 patients) are:

- Headache
- Dizziness
- numbness or tingling;
- sleepiness
- feeling or being sick
- loss of appetite
- stomach pain
- diarrhea
- upset stomach
- nausea
- vomiting
- flatulence (excessive gas in the digestive tract)
- dry mouth
- abnormal liver function tests
- rash
- weakness
- tiredness
- a decrease in white blood cells (that can increase the risk of infections)
- fever

- abnormal amounts of salts in the blood

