## **14.0 Economic Burden to Subjects**

### **14.1 Costs**

There will be no additional costs to the participants for enrolling on the trial.

- The study drug, posaconazole, will be provided at no cost to the study drug group participants while they take part in this study.
- The research-related tests and procedures that will be provided at no cost to the participants include:
  - CMP at Visits 1, 2, and 5, including blood draws (study drug group only)
  - 12-lead ECG at Visit 2 (study drug group)
  - Physical examination at Visit 2 (study drug group)
  - Microdialysis catheter and related reagents, and catheter monitoring at visits 3 through 6 both groups)
  - The removal of the microdialysis catheter will also be at no charge, performed at the bedside (both groups)

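### No blood count is planned while patients are on posaconazole, so a tolerability report without hematologic toxicity would mean that it was not systematically measured

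*Combined protocol and SAP*

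**What the plan says.** **Blood counts.** Section 7.2.1 lists "CBC and Comprehensive Metabolic Panel (which includes electrolytes, renal function and liver function) (approximately 2 teaspoons of blood" at Visit 1, done as routine care or taken from the medical record if within 31 days of consent. The schedule of events has one CBC entry, under Visit 1.

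**On-drug safety bloods.** Visit 2 specifies "Comprehensive Metabolic Panel (which includes electrolytes, renal function and liver function). Lab values within 1.5x institutional upper limit of normal are acceptable". Visit 5 (section 7.2.5, study drug group) specifies "Comprehensive Metabolic Panel (which includes electrolytes, renal function and liver function) (approximately 1 teaspoon of blood". The table of research samples in section 7.2.7 repeats "Comprehensive Metabolic Panel (which includes electrolytes, renal function and liver function) at Visits 1, 2, and 5", and section 14.1 funds "CMP at Visits 1, 2, and 5, including blood draws (study drug group only". Blood is also drawn at tumor resection (section 7.2.3, intra-operative procedure; section 7.2.5, plasma collection), but for drug concentration.

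**The hazard.** Section 10.0 puts "a decrease in white blood cells (that can increase the risk of infections" among the common side effects, defined there as at least 1 in 100 patients. Section 3.2 excludes from the drug arm "Patients who have previously had a severe side effect, such as agranulocytosis and neutropenia" on an earlier azole.

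**Use of the data.** Section 1.3 makes grade and frequency of adverse events under CTCAE v5.0 the first secondary endpoint. Section 8.3 adds that laboratory assessments will be described by the same criteria, "with separate descriptions for grade 3 or 4 laboratory abnormalities". Section 18.7 stops accrual after two or more unacceptable toxicities, meaning death or grade 4 toxicity directly attributed to drug. Section 9.3 says drug safety will be evaluated by clinical assessments and the laboratory tests in section 7.2.

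**The concern.** A white-cell decrease is a laboratory finding and cannot be graded without a count. The plan names this effect as common and treats a history of it as a reason for exclusion, but schedules no test for it after the first dose. Liver enzymes and QTc are both followed on drug, and no reason is given for treating white cells differently.

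The interpretation of the tolerability result is at stake. A table with no hematologic abnormalities would read as reassurance, in a population in which section 10.0 says the drug has not been tested, and in a trial that section 8.2 uses to support later-phase studies. The grade 4 stopping rule has the same gap: no scheduled test would reveal a silent grade 4 neutropenia.

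A second feature adds to this. Sections 7.2.2, 7.2.5 and 18.2 treat laboratory values within 1.5 times the upper limit of normal as acceptable and not as adverse events. That rule looks only upward. Read literally, a low white count satisfies it, so even a count obtained by chance might not be recorded as an adverse event.

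**Working it through.** The protocol gives no figure to reproduce: section 8.2 says the sample size rests on affordability. The check is a comparison of the schedule with the analysis, followed by a calculation for scale.

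**1. Planned safety bloods in the drug arm**

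| Time point | CBC | Metabolic panel |
|---|---|---|
| Visit 1 (before drug) | yes | yes |
| Visit 2 (day 3 ± 2) | no | yes |
| Visit 3 (surgery) | no (research blood drawn for drug level) | no |
| Visit 4 | no | no |
| Visit 5 (post-op day 1, last dose) | no | yes |
| Visits 6 and 7 | no | no |

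That is 1 count before drug and 0 on or after drug. The metabolic panel is described as electrolytes, renal function and liver function, so it does not supply a white count.

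**2. Exposure without a count.** Section 7.2.1 gives 168–240 hours of preoperative dosing: 168/24 = 7 days to 240/24 = 10 days, plus the dose on postoperative day 1. (Section 7.4.6.3 gives about 130–155 hours for the start of the outpatient supply. Those passages need reconciling, but the number of on-drug counts is 0 under either.)

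**3. What existing draws could supply**
- Visits 2 and 5: at most 2 values × 5 patients = 10. The schedule omits Visit 2 if surgery falls within 3 days.
- Adding the resection draw: at most 3 × 5 = 15.
- Timing: Visit 2 falls between day 1 and day 5, so it may precede a decline. Visit 5 is after surgery. The resection draw comes closest to the end of preoperative dosing.

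**4. What complete counts would show.** With 5 treated patients and true rate p, the chance of at least one case is 1 − (1 − p)^5. Only the 1% figure comes from the documents, as the floor for a common effect. The other rates are assumptions.

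| True rate p | 1 − (1 − p)^5 |
|---|---|
| 1% | 1 − 0.99^5 = 4.9% |
| 5% | 1 − 0.95^5 = 22.6% |
| 10% | 1 − 0.90^5 = 41.0% |
| 20% | 1 − 0.80^5 = 67.2% |

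These chances require that counts are taken. Under the present schedule, detection depends on routine care or symptoms, with no planned denominator.

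**5. A related inconsistency.** Section 7.2.1 lists the Visit 1 CBC as routine care without limiting it to one arm. The schedule of events marks CBC as study drug group only and does not carry the routine-care mark. Under the schedule, controls have no planned baseline count.

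**The case against.** The strongest reply is that adverse-event capture is not confined to scheduled research bloods. Section 9.1 records any adverse event whatever its severity or cause, section 18.3 has the investigator review abnormal test findings, section 18.2 has staff ask open questions at every visit, and section 8.3 will describe clinically significant laboratory abnormalities. A routine perioperative count could enter by these routes. This stands. A reader might infer that a white-cell decrease cannot be seen at all, and the documents do not support that. They support only that no planned assessment looks for it, and no section plans to collect later routine counts.

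It is also fair that section 8.3 describes the laboratory assessments that are taken and does not promise hematology. This is a choice of monitoring panel and not a contradiction. The panel fits the protocol's emphasis on liver eligibility limits and on hepatic, gastroenterological and renal toxicity in section 18.2. The choice still limits what the tolerability report can say, and the protocol does not acknowledge that limit.

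Two further inferences should be resisted. Section 10.0 quotes a 1% infection risk for the microdialysis catheter, but nothing in the protocol links that figure to white-cell count. And the 1 in 100 floor has no stated exposure duration, so it is not a rate for 7–10 days of dosing.

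Finally, added counts would be imperfect. Dexamethasone (permitted under section 7.2.1) and surgery complicate their reading, and the baseline may be a month old. These are reasons to record counts in both arms and to interpret them with care. They do not make the absence of counts informative.

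**Conclusion.** The point holds as a gap in ascertainment. No on-drug CBC is planned, so an absence of hematologic toxicity in the tolerability report, or under the grade 4 stopping rule, would mean that it was not systematically measured. It could not be read as not having occurred.

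The size is modest. The endpoint is secondary and descriptive, involves 5 treated patients, and is not among the success criteria in section 8.2. The primary pharmacokinetic result is unaffected. At the 1% floor, full monitoring would show at least one case in 4.9% of such trials, so the benefit is valid ascertainment and individual safety, not rate estimation. That figure assumes independent patients, a count from each of the 5, and a rate that applies to this exposure. The change is worth making because it is cheap. The conclusion about the schedule itself rests on no assumed rate.

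**What to change.** 1. **Add the test.** In sections 7.2.2 and 7.2.5, the research sample table in 7.2.7, the schedule of events and section 14.1, add a CBC with differential to the drug-arm draws at Visits 2 and 5. Preferably add it also to the blood draw at tumor resection (sections 7.2.3 and 7.2.5). The resection sample is specified as a heparin tube spun for plasma, so a count would need its own tube.
2. **Collect what routine care provides.** Record routine perioperative CBCs through Visit 7 in both arms, so that the effects of surgery and dexamethasone can be considered.
3. **Analyze it.** In section 8.3, include hematology in the CTCAE description against baseline, and report how many patients had an on-drug count.
4. **Close the one-sided rule.** In sections 7.2.2, 7.2.5 and 18.2, state that the rule of 1.5 times the upper limit of normal does not apply to low counts.
5. **Reconcile the baseline.** Make section 7.2.1 and the schedule agree on which arm has the Visit 1 CBC and whether it is routine care, so that controls have a baseline.
6. **If no CBC is added,** state in section 8.3 that hematologic toxicity was not systematically assessed.

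Cost: at most 10 assays at Visits 2 and 5, or 15 with the resection draw, plus some record abstraction and updated blood volumes. No new visit or venipuncture is needed.

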## 2.3

### Study Rationale

Both ketoconazole and posaconazole are FDA-approved anti-fungal agents with a well-established side effect and safety profile. Ketoconazole and posaconazole have shown efficacy in reducing tumor cell proliferation in our *in vitro* studies. Furthermore, both have also shown efficacy, mediated at least in part through inhibition of HK2 activity, in our animal models with dosing concentration and schedules that are documented as safe in humans.[58] As a drug, posaconazole has a more predictable half-life than ketoconazole and has less off-target effects. Therefore, the proposed trial will focus on the role of posaconazole exclusively. As a first step, demonstration of adequate penetrance of study drug in brain and tumor tissue (pharmacokinetics) and biological effect (inhibition of glycolysis and subsequent tumor cell death) is necessary prior to large scale clinical studies. A total of 5 control participants will be included in this study as we specifically want to assess for pharmacodynamic differences too. The

addition of a control group to this study rather to both the studies (ketoconazole study is a separate protocol) is because we feel posaconazole may be a more promising drug for moving forward.

Plasma drug concentration measurements are an unreliable method to assess delivery of drugs across the blood-brain barrier. In contrast, intracerebral MDC monitoring allows for approximate measurements within extracellular fluid (ECF) sampling of the brain. MDC placement within the brain is not a novel technique and has been utilized routinely in the ICU setting to measure brain metabolism by sampling of ECF of traumatic brain injury patients [59-61].

MDC are now FDA-approved and are being placed routinely with intracranial pressure monitors. This method allows for continuous measurement of ECF within a tumor or normal tissue. The dialysis probe has a semipermeable membrane which is less than 1 mm in diameter into which two sections of microcatheter are fused. Previous studies have demonstrated the feasibility of keeping the catheters in place of critically injured patients for up to 2 weeks [62-64].

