## 3.0 Inclusion and Exclusion Criteria

### 3.1 Inclusion Criteria

Patients eligible for enrollment in this study will be male and female adults with a presumed diagnosis of primary or recurrent HGG based on standard of care imaging (contrast-enhanced MRI) and clinical presentation and for whom surgical intervention has been selected as the most appropriate treatment option by the treating physician and patient.

1. Age  $\geq 18$  years
2. Evidence of primary or recurrent HGG that in the opinion of the treating team would require surgical resection
3. Adequate liver function defined as ALT, AST, ALP within 1.5x institutional upper limit of normal (for study drug arm only)
4. Ability to swallow medication (for study drug arm only)
5. Women of child-bearing potential and men must agree to use adequate contraception (hormonal or barrier method of birth control; abstinence) for the duration of study participation (for study drug arm only)
6. Ability to understand and willingness to sign a written informed consent document
7. Be able to comply with treatment plan, study procedures and follow-up examinations

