## 7.2 Study Procedures

If the patient appears to be eligible for the study, based on the initial evaluation, the study will be described to the patient and they will be given a chance to ask any additional questions. If the patient agrees to volunteer for the study, informed consent will be obtained.

If the patient is not eligible for enrollment in the study drug arm (e.g. contraindications to posaconazole, possible drug-drug interactions), they will be assessed for candidacy in the ketoconazole study, which has a separate IRB-approved protocol (IRB# STUDY00014115). If enrollment in the ketoconazole study is already completed or if the participant is not a candidate for ketoconazole either, then they will be considered for possible candidacy in the control arm. If, in this scenario, 5 participants have already been enrolled in the control arm, then the patient will not be a candidate for this study.

If the subject is deemed ineligible or wishes to not proceed with enrollment, then the delegated research coordinator or specialist will document the reason the subject was not enrolled in the trial and will update the site screening log appropriately.

A screening log will be used to store information from all potential participants screened. Information collected on the screening log will include participant initials, demographics (gender, race), date of consent, checkbox to note if signed informed consent given to subject, checkbox to indicate if subject enrolled, and reason for exclusion if subject not enrolled. The screening log will be kept in the regulatory binder by the study principal investigator to monitor study accrual.

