### **Control group**

Participants will first be considered for enrolment in the posaconazole arm. If there are contraindications to posaconazole, or if enrolment in posaconazole arm has been completed, then subjects will be enrolled in the ketoconazole study, which has a separate IRB-approved protocol (IRB# STUDY00014115). If enrollment in the ketoconazole study is already completed or if the participant is not a candidate for ketoconazole either, then they will be considered for possible candidacy in the control arm.

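### The lactate/pyruvate go criterion is met by any numerical reduction against five non-randomized controls, who are posaconazole-ineligible or overflow patients, and its comparison is not clearly defined

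*Combined protocol and SAP*

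**What the plan says.** Section 7.1 describes a single-center, open-label, non-randomized Phase 0 trial with five patients on posaconazole and five controls. Section 2.3 gives the reason for the controls: "A total of 5 control participants will be included in this study as we specifically want to assess for pharmacodynamic differences too".

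Sections 4.2.4, 7.2 and 7.2.1 describe two ways into the control arm.

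- **Ineligibility.** Section 7.2: "If the patient is not eligible for enrollment in the study drug arm (e.g. contraindications to posaconazole, possible drug-drug interactions". Section 7.2.1: "If any of routine tests or liver function tests are outside the acceptable ranges for the study, they will be assessed for candidacy". These patients are assessed for the ketoconazole study first. If that study is full, "or if the participant is not a candidate for ketoconazole either, then they will be considered for possible candidacy in the control arm".
- **Overflow.** The Control group paragraph of 7.2.1 sends patients down the same path "If there are contraindications to posaconazole, or if enrolment in posaconazole arm has been completed".

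Several eligibility criteria bind the treated arm only. Inclusion item 3 requires liver enzymes "within 1.5x institutional upper limit of normal (for study drug arm only". Exclusion item 4 reads "Patients with a history of acute or chronic hepatitis (for study drug arm only". Exclusion items 5 (liver enzymes) and 9 (adrenal insufficiency) carry the same restriction.

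Section 8.2 joins three go criteria with AND:

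1. A tumor drug concentration of at least 5 µM in at least 2 of 5 patients.
2. Lower average lactate and pyruvate than controls, in both tumor and dialysate.
3. Steady lactate and pyruvate over 24 hours in controls.

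Criterion 1 is worded for either of two drugs and for each arm. Criterion 2 refers to treated cohorts in the plural. Section 8.3 plans descriptive pharmacodynamic summaries, to be compared with control levels.

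The screening log in 7.2 holds the consent date and a "checkbox to indicate if subject enrolled, and reason for exclusion if subject not enrolled".

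**The concern.** Criterion 2 is the only one of the three that compares treated patients with controls, so it carries the pharmacodynamic part of the decision to proceed or to fail early. It is a bare comparison of averages from five patients against five. It can be met with no effect on glycolysis, or missed despite one. The cause could be chance, or a difference in who could become a control.

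Three further gaps make the result hard to read.

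- The log keeps a reason only for patients who were not enrolled. No stated record shows why an enrolled control was not treated.
- The mention of two drugs and several cohorts leaves open whether the ketoconazole patients count in the comparison.
- The descriptive comparisons of HK2 activity, proliferation, cell death, angiogenesis and metabolites rest on the same five controls.

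**Working it through.** **The plan's own figure.** The total of 10 is 5 + 5. Section 8.2 says the size rests on affordability and not on statistical grounds, so there is no power calculation to reproduce.

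**Inputs from the documents.** Five patients per arm. Four averages must all be lower (two metabolites in two matrices). No margin is set.

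**Assumptions.** The documents give no standard deviation (SD), correlation or selection effect. I take normal means, equal SDs and a common correlation ρ among the four treated-minus-control differences.

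**Chance of meeting criterion 2 with no drug effect.** The standard error (SE) of one difference is SD × √(1/5 + 1/5) = 0.632 SD. If selection alone makes controls higher by δ SD, then

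P(all four lower) = ∫ φ(u) · Φ[(δ/0.632 − √ρ·u)/√(1−ρ)]⁴ du.

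For δ = 0 and ρ = 0 this is 0.5⁴ = 0.0625.

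| Selection shift δ | ρ = 0 | ρ = 0.5 | ρ = 0.8 |
|---|---|---|---|
| none | 0.0625 | 0.200 | 0.314 |
| controls 0.5 SD higher | 0.381 | 0.532 | 0.637 |
| controls 0.5 SD lower | 0.002 | 0.038 | 0.093 |

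With no shift, the figure approaches 0.5 only as ρ approaches 1 (0.487 at ρ = 0.999). The 0.5 SD shift is illustrative and is not in the documents. It shows only that selection can act in both directions.

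**Jointly with criterion 1.** P(at least 2 of 5) = 1 − (1−p)⁵ − 5p(1−p)⁴, where p is the per-patient chance of reaching 5 µM. For assumed p = 0.2, 0.5 and 0.8 this is 0.263, 0.813 and 0.993. Multiplying by 0.200 (ρ = 0.5, no shift, independence assumed) gives 0.053, 0.163 and 0.199. Criterion 3 can only lower these.

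**Does the reading of the treated cohorts matter?**

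- *Pooling five ketoconazole patients (10 v 5).* The SE becomes √(1/10 + 1/5) = 0.548 SD. The no-shift figures stay at 0.0625, 0.200 and 0.314.
- *Each cohort must be lower than the shared controls on all four averages.* At ρ = 0 the chance is (1/3)⁴ = 0.012. By simulation it is about 0.08 at ρ = 0.5 and 0.165 at ρ = 0.8.

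The two readings therefore give different rules, and the plan does not choose between them.

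**What an interval would show at 5 v 5.** The 95% half-width is t(0.975; 8 df) × 0.632 = 2.306 × 0.632 = 1.46 SD. For an assumed coefficient of variation (CV) of 30% or 60%, the log-scale SD √ln(1 + CV²) is 0.294 or 0.555. The ratio's interval is then the estimate times or divided by exp(1.458 × 0.294) = 1.53 or exp(1.458 × 0.555) = 2.25. A two-sided 5% t test on one metabolite has power 0.286 at a true 1 SD reduction and 0.791 at 2 SD.

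**Data available for controls.** Section 7.2.1 lists CBC, a metabolic panel, history and medication review as routine at Visit 1 for every consented patient. The schedule of events marks the metabolic panel as drug-group only, but that row can be read as the separate research draw (7.2.1 and 14.1). The drug-group-only mark on CBC has no such explanation and disagrees with 7.2.1.

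**The case against.** The trial is openly a non-randomized, exploratory Phase 0 study. Its size is set by affordability and its pharmacodynamics are descriptive. The primary endpoint, the drug AUC, does not use controls. All of that stands and limits the weight of the point. It does not remove it, because section 8.2 makes this comparison part of a decision rule.

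A reader might infer four stronger things that the documents do not support.

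- *That a numerical metabolite reduction is enough for a go.* It is not. Three criteria must all be met, and criterion 2 itself needs both metabolites lower in both matrices.
- *That the controls are biased.* No passage shows that ineligibility changes lactate or pyruvate. The share of controls by route is not given, and it depends partly on a ketoconazole study that cannot be seen here. Exclusion item 12 also lets the investigator exclude, in either arm, a condition or laboratory abnormality that could disturb interpretation, although it is discretionary and has no threshold.
- *That the drug-arm-only liver, hepatitis and adrenal criteria should be extended to controls.* Those criteria are tied to receiving the drug, which controls do not. Extending them would shrink a pool that must supply five controls and tilt it toward later overflow patients, trading one unproven difference for another.
- *That the drug-group-only medication review at Visit 3 contradicts 7.2.1.* Section 7.2.1 covers Visit 1 only, and there the schedule agrees with it.

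It is also fair to say that reporting an interval leaves the 6% to 31% unchanged. The interval changes how a met criterion is read, not how often it is met.

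**Conclusion.** The point holds for the control-comparison criterion, not for the go decision as a whole. Criterion 2 is satisfied by any reduction in averages against five non-randomized controls. With no drug effect and no selection difference it is met alone about 6%, 20% or 31% of the time at ρ = 0, 0.5 or 0.8. Combined with criterion 1 at ρ = 0.5, the figure is about 5% to 20% before criterion 3. These figures assume normal means, equal SDs and the stated correlations; the joint figure also assumes independence and p between 0.2 and 0.8.

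The direction and size of any selection effect are unknown, so the shifted rows of the table must not be read as estimates of bias. Separately, section 8.2 does not define which patients form the treated side of the comparison. This should be corrected because it changes what the trial can conclude about drug effect.

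**What to change.** **(a) Section 8.2.** Define criterion 1 for posaconazole in the study drug arm. Define criterion 2 as posaconazole against this study's controls, with no pooling of the ketoconazole cohort.

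**(b) Sections 8.2 and 8.3.** Report the posaconazole/control geometric mean ratio with a 95% confidence interval for each metabolite in each matrix. Use one value per patient: average samples or catheters of the same tissue type first, and compare dialysate within the same catheter location. Present these intervals with criterion 2 in the go decision. State that the comparison is non-randomized and that a reduction in averages alone is not evidence of a drug effect. The interval need not exclude 1: at 5 v 5 that hurdle would be passed only 29% of the time for one metabolite with a true 1 SD reduction.

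**(c) Sections 7.2 and 8.3.** Record and report each control's reason for not being in the drug arm (the specific ineligibility, or overflow) and the enrolment date. List baseline liver tests and concomitant drugs by arm from data that 7.2.1 already collects, showing ineligible and overflow controls separately. Reconcile the CBC marking in the schedule of events with 7.2.1.

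**Cost.** A text amendment and slightly more analysis, with the same 10 patients and no extra blood draw. The intervals will be wide, about ±1.46 SD with five per arm and wider where a catheter location has fewer patients. The pharmacodynamic result will look less certain, which is an accurate picture of what five against five can show.
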